Mirpur is a part of the Dhaka metropolitan area with an estimated population of over 2.5 million people. Different socio-economic groups of communities, such as low, middle income, and high income, live in the area. The icddr, b hospitals treat more patients from Mirpur than from any other part of Dhaka. Mirpur is divided into 16 wards of the Dhaka City Corporation. We have selected 9 wards in Mirpur (7-13, 15 and 41) for the study. The selection has been based on the high number of cholera patients from these wards visiting the icddr, b hospitals over the last few years (2008-2010). It was observed that most of the cholera patients were living in overcrowded households with low income, poor sanitation, unsafe and shared water usage, and general poor living conditions. In preparation for this "Single Dose Cholera Vaccine Trial (SCVB)" trial we will commission a census of these high cholera incidence wards in Mirpur. These wards are separated from the other wards where the feasibility study of the oral cholera vaccine "Introduction of Cholera Vaccine in Bangladesh (ICVB)" is being carried out (Figure 1) by a 300 meter buffer zone. This buffer zone will help minimize contamination between two study areas. First, the census team will create geographic information system (GIS) database by digitizing buildings and other structures in the target wards using satellite derived images. The digitized buildings and structures will be verified for ground verification. The census team will visit each building and ascertain whether or not people are living in the building. If people reside in the building, the census team will assess whether the residential structures are overcrowded, have poor sanitation and drainage, unhealthy living conditions, and/or share water among several families in order to assess high risk groups [28].

Based on this survey, the team will assess whether the people living in each building/structure are a high risk group or not. If the residence meets these criteria, as described above, the census team will collect verbal consent from the respondent and other information about the household (Appendix 1Ai, 1Aii, 1Aiii, 1Aiv). The supervisors will also subsequently check whether this assessment fulfills the requirement for defining them as a high risk population. We will conduct a *de jure* census and will enumerate 324,178 high risk residents from the target wards.

[figure not shown]

Figure 1. Study Area

Study Procedure and methodology

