- Date of onset for first episode of watery diarrhea with severe dehydration detected in the study treatment centres from 7days to,6, 12,18and 24 months, respectively after dosing among those who received 1 dose of vaccine or placebo
- Date of onset for first episode of diarrhea with fecal excretion of *V. cholerae*O1 in non-participating subjects, who are detected within one of the study treatment centres from 7 daysup to 6,12,18and 24 monthsafter dosing of study participants.
- Date of onset for first episode of diarrhea with severe dehydration and fecal excretion of *V. cholerae*O1 in non-participating subjects, who are detected within one of the study treatment centres from 7 daysup to 6,12,18and 24 monthsafter dosing of study participants.

Secondary safety endpoints

- Number of adverse events and serious adverse events in participants who received 1 dose of vaccine or placebo and present for care of vaccine adverse effects at treatment settings or who die from the time of dosing until 28 days later (passive surveillance by type of complaint and by cause of death).

Secondary immunogenicity endpoints

- Geometric mean serum vibriocidal (to El Tor Inaba and Ogawa O1 serogroup organisms and to O139 serogroup organisms) titers measured in participants at baseline (day0) and 14 days after receipt of either vaccine or placebo.
- Four-fold or greater rises in titers of serum vibriocidal antibodies (to El Tor Inaba and Ogawa O1 serogroup organisms and to O139 serogroup organisms), relative to baselineday 0 and 14 two days after receipt of either vaccine or placebo

Analysis plan

To analyze vaccine protection, we will use Cox proportional hazard regression models verifying first that the proportionality assumption is satisfied for all independent variables. Checking of the proportional hazard assumption will be performed by plotting the observed standardized score with simulated realizations for each covariate in the model, and the p-value will be derived from the Kolmogorov-type supremum test based on 1,000 simulations. If a variable does not satisfy the proportionality assumption, then we will exclude the variable from the model. However, the critical variables such as vaccination status and age will be kept in the model irrespective of the results of the test for proportionality assumption.

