The outcome will be the time to event of the onset of the first episode of cholera. Hazard ratios (HRs) of the target outcome in the vaccine versus placebo groups will be estimated by exponentiating the coefficient for the vaccine variable (independent variable) in these models, and vaccine efficacy is estimated as $[(1 - \text{HR}) \times 100\%]$. Standard errors for the coefficients will be used to estimate P values and 95% confidence intervals for the HRs. Kaplan-Meier cumulative event free survival curves for patients assigned to vaccine and placebo groups will be prepared for descriptive purposes.

Simple analyses of vaccine impact will be performed. Final adjusted estimates will be obtained from models that included the covariates found to be independently associated with the time to the event at $P < 0.1$ in a backward selection algorithm. To evaluate heterogeneity of vaccine protection among different subgroups, we will evaluate interaction terms between the vaccination and subgroup variables in these models. The threshold for significance in the primary analysis will be set at $p < 0.05$ (one tailed) and 95% CIs (lower bound) will be calculated. In all other analyses, the threshold for significance will be set at $p < 0.05$ with two-tailed analysis.

Primary Analysis at 6 months of follow-up:

Primary analysis will be planned at 6 months following dosing. In addition, we will estimate the protective impact of vaccination against culture-proven *V. cholerae* O1 diarrhoea episodes severe enough to require treatment in a health care facility; age-specific protective efficacy; indirect and age-specific indirect vaccine protection using a GIS approach described elsewhere (Ali et al 2005); overall and age-specific overall and total vaccine protection; culture-proven *V. cholerae* associated with severe dehydration (the definition is in Appendix 12); and episodes of acute watery diarrhoea severe enough to require treatment in a health care facility; episodes of acute watery diarrhoea irrespective of severity. Seroconversion in the vaccine and control groups will also be compared. Statistical methods for these secondary analyses will be the same as those used in the primary analyses contingent on an adequate number of cases.

Analysis at 6,12,18 and 24 months of follow-up:

Primary analysis is to be performed at 6 months. The following available time points (12,18 and/or 24 months) will be for secondary analysis points.

Surveillance for 24 months

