9. STATISTICAL METHODS

The primary analysis will address occurrence of cholera during six months of follow-up among vaccine and recipients. Cox proportional hazard regression models will be used, verifying first that the proportionality assumption is satisfied for all independent variables. Hazard ratios (HRs) of the target outcome in the vaccine recipients versus placebo recipients will be estimated by exponentiating the coefficient for the vaccine variable in these models, and vaccine protection will be estimated as $[(1 - HR) \times 100\%]$. Standard errors for the coefficients will be used to calculate one-tailed p values and 95% upper confidence intervals for the HRs.

[figure not shown]
Final adjusted estimates will be obtained from models including the variables which will be found to be independently associated with the time to the event at p value $< .10$ in a backward selection algorithm.

To evaluate heterogeneity of vaccine protection among different subgroups, interaction terms between vaccination and subgroup variables in these models will be evaluated. P values and 95% confidence intervals for these analyses will be calculated as two-tailed.

[figure not shown]
Appendix1. CONSORT for assembling population for the primary analysis

[figure not shown]
[figure not shown]
Appendix2. Episode classification (primary endpoint)

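### Indirect (neighbourhood-coverage) protection inherits the primary Cox standard errors, with no allowance for clustering of cholera risk among neighbours

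*Supplement*

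**What the plan says.** In the latest protocol, Data Analysis, under the primary analysis at 6 months, the further analyses include "indirect and age-specific indirect vaccine protection using a GIS approach described elsewhere". The paragraph ends: "Statistical methods for these secondary analyses will be the same as those used in the primary analyses contingent on an adequate number of cases".

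The primary method is in the Analysis plan subsection: "To analyze vaccine protection, we will use Cox proportional hazard regression models", and "Standard errors for the coefficients will be used to estimate P values and 95% confidence intervals for the HRs". SAP section 9 has the same structure: "Standard errors for the coefficients will be used to calculate one-tailed p values and 95% upper confidence intervals for the HRs". For analyses other than the primary one the protocol says "In all other analyses, the threshold for significance will be set at" 0.05, two-tailed.

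Neither document mentions a sandwich variance, a cluster or household term, frailty, a permutation test or spatial correlation. SAP sections 6.1 and 6.2 cover direct protection only, so the SAP supplies no separate method for indirect protection. Section 7 lists the percentage of vaccinees within 100 m of the household, but only as a candidate covariate.

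The Study population section says most cholera patients lived in overcrowded households with "low income, poor sanitation, unsafe and shared water usage, and general poor living conditions".

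**The concern.** Vials are randomised to individuals, so vaccine and placebo recipients live side by side. Neighbourhood risk is common to both arms and largely cancels from the comparison. Standard errors that treat people as independent are then adequate.

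Indirect protection has a different kind of exposure: how much of the surrounding population was vaccinated. People who live close together share nearly the same value. If they also share cholera risk through water, sanitation and crowding, the effective amount of information lies closer to the number of neighbourhoods than to the number of people. An independence-based test of no coverage effect can then reject simply because cases cluster. This is separate from confounding: it occurs even when coverage is unrelated to underlying risk.

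At stake are the p values and 95% intervals for indirect and age-specific indirect protection. Chance clustering could be reported as significant herd protection, or harm, after a single dose.

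**Working it through.** **1. The plan's own sample size.** Inputs from the protocol's sample size section: placebo incidence p2 = 0.00056 per 6 months, R = 0.5 (so p1 = 0.00028), R0 = 0.90, k = 0.5, one-sided alpha 0.05, power 0.80.

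N = (z_α + z_β)² [q1/(k p1) + q2/((1−k) p2)] / (log R0 − log R)² = 191,659, against the stated 191,660. Allowing 6.25% attrition, 191,660 / 0.9375 gives the stated 204,438, or 102,219 per arm. The inputs reproduce. No figure is stated for indirect protection.

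**2. Expected placebo cases at 6 months.**
- After attrition: (191,660 / 2) × 0.00056 = 53.7.
- Before attrition: 102,219 × 0.00056 = 57.2.

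**3. Variance inflation.** Take G equal neighbourhoods, half with high and half with low coverage, with m expected cases each. Let neighbourhood risk have coefficient of variation CV and be unrelated to coverage. The variance of a neighbourhood count is m + m²CV², so relative to the independence variance the inflation is

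DEFF = 1 + m × CV², with m = cases / G.

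The true size of a nominal two-sided 5% test is 2[1 − Φ(1.96 / √DEFF)], and honest intervals are wider by √DEFF on the log scale.

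G and CV are **assumptions**; the documents give neither. Simulation used 40,000 replicates per setting, gamma-distributed risk, Poisson cases and a Wald test of the log rate ratio, which approximates Cox for rare events. No covariates were included.

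At 6 months, with 53.7 placebo cases:

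| G | CV | DEFF | True size, formula | True size, simulated |
|---|---|---|---|---|
| 50 | 0.5 | 1.27 | 8.2% | 7.6% |
| 50 | 1 | 2.07 | 17.3% | 16.6% |
| 100 | 0.5 | 1.13 | 6.6% | 6.0% |
| 100 | 1 | 1.54 | 11.4% | 10.6% |
| 200 | 0.5 | 1.07 | 5.8% | 5.5% |
| 200 | 1 | 1.27 | 8.2% | 7.9% |
| 500 | 0.5 | 1.03 | 5.3% | 4.8% |
| 500 | 1 | 1.11 | 6.3% | 5.9% |

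With CV = 0 the simulated size is 4.6 to 4.7%, so the test is sound when there is no clustering.

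**4. Longer follow-up.** If cases at 24 months are four times those at 6 months (assumed), the formula at CV 1 gives 39.4%, 26.9%, 17.3% and 10.1% for G = 50, 100, 200 and 500.

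**5. Does clustering the variance help?** With 57 cases and CV 1, the uncorrected size is 17%, 11% and 8% for G = 50, 100 and 200. With neighbourhood-clustered errors it is 7%, 6% and 5%.

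**6. The direct comparison.** With individual randomisation inside the same clustered populations, the simulated two-sided size was 4.8 to 4.9%.

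**The case against.** Several points on the other side stand, and they limit the claim.

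- **The GIS method is cited to an outside source**, which may have its own variance method. The sentence on common methods is also loose: its list includes seroconversion, which is not a time-to-event analysis. And a standard error of a coefficient need not mean a model-based one. Still, that sentence is the only statement on inference for indirect protection, and its ordinary reading is the independence-based error.
- **The exposure is not fully defined.** The explicit contrast of placebo recipients in high- and low-coverage neighbourhoods appears only in the reply to an external referee of version 1. The non-participant endpoints (cases "in non-participating subjects, who are detected within one of the study treatment centres") are nowhere said to be compared by local coverage, so they are affected only if that is done.
- **Covariate adjustment may absorb part of the clustering.** SAP section 7 offers water source, sanitation, hand washing and expenditure, plus safe-water coverage, sanitation coverage and population density within 100 m. The calculations above are unadjusted. Residual correlation after adjustment is unknown.
- **The neighbourhoods may be numerous.** A 100 m circle covers π × 0.1² = 0.031 km². If the study area were 6 to 12 km² (assumed), it would hold about 190 to 380 of them. With 57 cases the size is then 5.4 to 5.9% at CV 0.5 and 6.8 to 8.6% at CV 1. The larger figures need risk correlated well beyond 100 m.

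A reader might infer that the indirect-effect tests certainly reject at two or more times the nominal rate. The documents do not support that: it holds only for some combinations of inputs they leave open.

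**Conclusion.** The point holds in a conditional form. As written, the protocol carries the primary Cox standard errors over to indirect protection and makes no allowance for correlated risk among neighbours. The protocol's own description of crowding and shared water makes some positive correlation likely. To the extent that it survives covariate adjustment, p values will be too small and intervals too narrow.

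At 6 months, with about 54 to 57 placebo cases, the true size of a nominal 5% test is roughly 5 to 9% for about 200 to 500 neighbourhoods and CV 0.5 to 1. It is 11 to 17% for 50 to 100 neighbourhoods at CV 1. It rises as cases accrue to 24 months, and is smaller within age strata, which hold fewer cases. All of these rest on assumed G and CV, on coverage unrelated to risk, and on no covariate adjustment.

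A reader might also infer that the primary efficacy result is at risk. It is not: the vaccine-versus-placebo test keeps its nominal size because allocation is individual. The defect is confined to secondary analyses, but is worth mending because a herd-protection claim for a single dose could rest on them.

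**What to change.** Amend the protocol paragraph on secondary analyses along these lines: *The direct vaccine-versus-placebo analyses use the Cox model and its model-based standard errors as stated. For indirect protection, and for any other analysis whose exposure is neighbourhood coverage, p values and 95% confidence intervals will come from covariate-adjusted models with a variance clustered on a geographic unit (robust sandwich, or a shared frailty for that unit). The unit will be fixed before unblinding and will be larger than the coverage radius.*

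State the coverage exposure and its radius in the same place. Carry the text into the SAP if the indirect analysis is added there.

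The cost is a sentence or two and a software option; the GIS locations are already collected. The downside is wider intervals for indirect effects, by √DEFF: a factor of about 1.44, 1.24 and 1.13 for 50, 100 and 200 neighbourhoods at CV 1. With as few as 50 units the sandwich error remains slightly liberal (about 7% in the check above), so the unit should not be made coarser than necessary.

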An Individually randomized, placebo-controlled trial to measure the protection conferred by a single dose regimen of live-attenuated, killed, whole cell oral cholera vaccine (Shanchol) in Dhaka, Bangladesh.

**DETAILED BUDGET FOR BUDGET PERIOD
DIRECT COSTS ONLY**

Cost Categories	FROM 01 Jan. 2014 THROUGH 30 Jun. 2015			
	Year 1	Year 2	Year 3	TOTAL US\$
PERSONNEL				
International personnel	181,515	183,776	98,163	463,454
Local Personnel	1,390,098	1,173,277	550,263	3,113,582
SUBTOTALS PERSONNEL	1,571,613	1,361,997	648,426	3,582,036
CONSULTANT COSTS				
Consultants	67,440	70,288	0	137,728
SUBTOTALS CONSULTANTS	67,440	70,288	0	137,728
EQUIPMENT (itemize)				
EQUIPMENT	157,100	0	0	157,100
SUBTOTALS EQUIPMENT	157,100	0	0	157,100
SUPPLIES (itemize by category)				
Furniture & Stationeries	156,446	36,000	16,000	208,446
SUBTOTALS SUPPLIES	156,446	36,000	16,000	208,446
TRAVEL				
Local Travel	43,750	44,100	18,322	106,172
International Travel	23,400	34,320	18,876	76,596
SUBTOTALS TRAVEL	67,150	78,420	37,398	182,968
Other costs				
Training cost, printing, Rent, specimen testing, GIS vaccine delivery, good clinics practices etc.	345,325	193,300	66,200	604,825
Hospital cost				
icdsh, Mipur treatment centre and other health facilities cost	150,000	75,000	0	225,000
SUBTOTALS OTHERS	495,325	268,300	66,200	829,825
SUBTOTAL DIRECT COSTS	2,515,075	1,815,005	768,024	5,098,104
Overhead @15%	353,696	272,251	115,204	741,151
TOTAL Budget	2,868,771	2,087,256	883,228	5,839,255

[name]
Sr Budget Co-ordinator

Budget Justifications

Budget for the study is needed for carrying out vaccine delivery in the selected field sites of Mirpur area. Surveillance of the diarrheal patients coming from the study sites will be carried out at the hospitals and health facilities in Mirpur and icddr,b hospitals and microbiological tests carried out at icddr,b. Other important costs are for GIS activity, advocacy meetings, local and international travel, transportation of vaccine, programme monitoring, training, data management etc.

Personnel:

Personnel comprise core component, data management, census, GIS activity, vaccine delivery, census update, passive surveillance and quality team. Total amount budgeted under the categories is US \$3,582,036 for 30 month period.

Consultant costs:

The category consists of 2 external consultants and support for infrastructure amounting US\$ 137,728 in 24 months.

Equipment:

Various capital equipments are required for the study for data collection and laboratory support. All these equipment would be procured in year 1 amounting to US\$ 157,100

Supplies:

Supplies comprise of stationeries and furniture amounting to US\$ 208,446 in the 30 month period.

Travel:

Local travel in all years will require US \$106,372 for supervisory visit and data collection. International travel required in year 2 and year 3 amounting to US\$ 76,596 for study seminar/ workshops/meetings at national and international locations.

Vaccine delivery:

Vaccine delivery in the Mirpur site will be required in year 1 amounting to US\$ 50,000

GIS:

GIS mapping and licensing will be required in initial stages through a subcontract with a GIS company.

Other costs:

Other costs comprising training, printing and office rent, immunogenicity study, specimen testing (324 subjects) etc. amounting US\$ 554,826 in the 30 month period.

Hospital costs:

The costs for icddr,b, Mirpur treatment centre and other health facilities are US\$ 225,000 in the first 24 months of the study.

Overhead costs:

Overhead costs is calculated at 25% amounting to cover direct overhead costs (15%) as well as built in cost.

Check-List

**Check-list for Submission of Research Protocol
For Consideration of the Research Review Committee (RRC)
[Please check all appropriate boxes]**

1. Has the proposal been reviewed, discussed and cleared by all listed investigators?  Yes  No If the response is No, please clarify the reasons:
2. Has the proposal been peer-reviewed externally?  Yes  No  External Review Exempted If the response is "No" or "External Review Exempted", please explain the reasons: If the response is "Yes", please indicate if all of their comments have been addressed?  Yes (please attach)  No (please indicate reason(s)):
3. Has the budget been reviewed and approved by icddr,b's Finance?  Yes  No (reason): _____
4. Has the Ethics Certificate(s) been attached with the Protocol?  Yes  No If the answer is "No", please explain the reasons:

[name] Signature of the Principal Investigator
 
31/10/2012 Date

DATA ANALYSIS PLANS

2. SUMMARY OF THE ANALYTICAL PLANS

Objectives To evaluate protective efficacy of a single dose regimen of the bivalent, killed, whole cell oral cholera vaccine Shanchol™, given to healthy, non-pregnant residents aged one and above in Dhaka, Bangladesh, against culture-proven *V. cholerae* O1 diarrhea which has been detected in all treatment settings serving the catchment population with onset of 7 days to 6 months (180 days) after dosing

Design Two-arm individually randomized double-blind placebo-controlled trial

Subjects All enumerated healthy consenting subjects, residing in Wards 7-13, 15 and 41 of Mirpur, Dhaka, Bangladesh. Subjects will be included if they are permanent residents of the study site, not pregnant, and at least 1 year of age during vaccination.

Population size Approximately 350,000 subjects in the study area

Vaccination Period: January 10 to February 4, 2014

Agents Bivalent, killed, whole-cell oral cholera vaccine

End-points The primary endpoint for the study efficacy is the onset date of the first episode of culture-confirmed *V. cholerae* O1 diarrhea episodes detected in the study treatment centers with onsets of 7 days to 6 months (180 days) after dosing among those who have received one complete and correct dose of the vaccine or placebo.

Period of study 6 months post-receipt of either vaccine or placebo

3. POPULATION AND DEMOGRAPHIC EVENTS

A census was conducted by the project people during July 2012 to December 2013 to enumerate the study area population. The census captured the *de jure* population defined as persons who stated their residence in the study area was their regular residence. The population has been regularly updated thorough vital demographic events of the study area population. A close out census will be conducted after six months of follow-up.

Out-migrations (internal/external): Individuals who were present at zero time (defined in Chapter 5: Other definition),but migrated out any time after zero time.

Deaths: Individuals who were present at m but died any time after zero time.

For the analysis, we will follow the demographic date assignment flow chart (Appendix 5).

